 To evaluate the levels of ocrelizumab in the mother during pregnancy 	 Serum concentration of ocrelizumab in the mother during pregnancy (time frame of blood sampling: Week 24–30, Week 35) and at delivery (time frame of blood sampling: within 24 hours after delivery) 	
Safety Objectives		
• To evaluate the safety of ocrelizumab in the mother, and the safety of infants potentially exposed to ocrelizumab	 Rate and nature of adverse events in the mother throughout the study, including changes in clinical and laboratory results 	
	 Rate and nature of adverse events in the infant throughout the study, including infections and hospitalizations 	
To evaluate pregnancy and neonatal outcomes	 Proportion of pregnancies resulting in live births (term and preterm, with and without congenital anomalies), therapeutic abortions, or stillbirths 	
	Infant characteristics at birth, including but not limited to body weight, head circumference and length	

ASQ-3 = Ages and Stages Questionnaire, version 3; EDSS = Expanded Disability Status Scale; HBV = hepatitis B virus; Hib = Hemophilus influenzae type b; LLN = lower limit of normal; MMR = measles, mumps, and rubella; MS = multiple sclerosis; PCV-13 = 13-pneumococcal conjugate vaccine; SARS-CoV-2 = severe acute respiratory syndrome coronavirus 2; sNfl = serum neurofilament light chain; WHO = World Health Organization.

[
Objectives	Corresponding Endpoints
Exploratory Objectives	
 To evaluate the infant's growth velocity and developmental milestones in the first year of life 	 Assessment of growth velocity based on age-adjusted body length, weight and head circumference, using growth charts according to the WHO Child Growth Standards, as well as absolute values, at Months 2, 4, 6, 9, and 12
	 Assessment of child developmental milestones in the domains of communication, gross motor, fine motor, problem solving, and personal-social at Months 2, 4, 6, 9, and 12, using the ASQ-3
 To evaluate humoral immunity to clinically relevant pathogens in mothers during pregnancy 	 Mean titers of antibody immune response(s) to vaccinations, measured in the third trimester (time frame of blood sampling: Week 35.
	 Percentage of women with positive humoral response (seroprotective titers; as defined for the individual vaccine) to vaccines (time frame of blood sampling: Week 35.

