6.5 SAFETY ANALYSES

The safety analyses will be performed on the safety populations for the women and for the infants separately. The analyses will be conducted on data collected from enrollment until the end of the study.

The safety outcome measures will comprise the following: incidence and nature of all adverse events, including findings on vital sign measurements, neurological examinations, clinical laboratory tests, locally-reviewed MRIs conducted for safety reasons (non-MS CNS pathology), and concomitant medications.

Safety will be assessed through summaries of adverse events (including rates/incidence rates and corresponding 95% CIs) and clinical laboratory abnormalities.

All adverse events will be summarized by mapped term, appropriate thesaurus level and toxicity grade, and tabulated by MedDRA system organ class (SOC) and preferred term for individual adverse events within each SOC. Grade 3–5 adverse events, serious adverse event, adverse events leading to treatment discontinuation, and time to withdrawal from the study due to an adverse event will be summarized. In addition, all serious adverse events and deaths will be listed.

Associated laboratory parameters, such as hepatic function, renal function, and hematology values will be grouped and presented together.

The proportion of pregnancy outcomes including live births (term and preterm), therapeutic abortions and stillbirths will be calculated, and the corresponding two-sided Clopper-Pearson 95% CIs will be presented overall.

Concomitant medications recorded during the study will be summarized using frequency tables.

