4. STATISTICAL METHODS

The analysis of this open-label study will be primarily based on descriptive statistical methods. Unless otherwise specified, no statistical tests are planned. Corresponding 95% Cls will be presented as appropriate.

For continuous variables, descriptive statistics (e.g., number of patients [n], mean, standard deviation [SD], median, 25th and 75th percentiles, minimum, maximum) will be calculated and summarized.

For categorical variables, the number and percentage in each category will be displayed.

The analyses outlined in this Statistical Analysis Plan (SAP) supersede those specified in the protocol.

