4.8.1 Exposure of Study Medication

Ocrelizumab will not be administered post-baseline until the infant's birth. Treatment with commercial ocrelizumab may be resumed at any time after birth for women who decide not to breastfeed. Some women may decide to resume treatment with ocrelizumab whilst breastfeeding. For those women, treatment with ocrelizumab should be restarted after collection of the infant blood sample at Week 6 of life (±7 days) if possible, but the decision is left to the discretion of the woman and the investigator.

Definitions

Dose: Ocrelizumab dose is given as one infusion or two infusions administered 2 weeks apart. Women will be considered to have received a dose of treatment if at least part of one infusion of that Dose (either Day 1 or Day 15 for dual infusions) was given.

Treatment duration (in weeks) for woman received OCR will be calculated as follows: [(Date of last contact* - Date of first postpartum dose) + 1] / 7

*Earliest 1) date of last OCR dose plus risk window of 6 months (182 days)2) date of death3) Clinical Cut-off Date

Exposure Analysis

The following measures of exposure of ocrelizumab will be summarized in the SAFW using descriptive statistics:

- Number of patients completing each dose type (Dose 1, full dose; Dose 1 split dose #1; Dose 1, split dose #2, Dose 2, full dose; Dose 3, full dose)
- Treatment duration (weeks)
- Number of doses received (Day 1 and Day 15 infusions are considered as one dose)

• Total cumulative dose (mg)

A corresponding listing will be produced.

MS treatment postpartum

- Type of DMT including ocrelizumab use postpartum
- Time (months) between delivery and first postpartum ocrelizumab as continuous and categorical (0-3 months, >3 and ≤6 months, >6 months)
- Number of women who received ocrelizumab dose postpartum
- Number of ocrelizumab doses postpartum
- Time (months) between first and second postpartum ocrelizumab dose

4.8.2 Adverse Events

All summaries of AEs will be presented separately for women and infants based on the respective Safety population. Adverse events will be presented overall and by timepoint (defined below). AEs will also be presented for subgroups based on OCR exposure prior to the study as list below, for infants and women separately:

- In 3-month interval of before/during pregnancy (3-6 months before LMP, 0-3 months before to LMP, during the 1st trimester)
- ≥3 months before to LMP vs <3 months prior to LMP and/or during pregnancy

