For each recorded adverse event (AE), the term entered by the investigator describing the event (the "reported term") will be assigned a standardized term (the "Preferred Term" [PT]) and assigned to a superclass term (the "System Organ Class" [SOC]) on the basis of the MedDRA WHO dictionary of terms version 26.1.

Definitions

Infant AE timepoints:

Neonatal (<28 days): AEs with an observed or imputed date of onset before the first 28 days of life.

Infant (≥28days): AEs with an observed or imputed date of onset on or after the 28 days of life.

Women AE timepoints:

Pregnancy: AEs with an observed or imputed date of onset before the infants' birth, i.e. during pregnancy. An AE with a completely missing, non-imputed start date will be assumed to be a pregnancy AE.

Pre-ocrelizumab postpartum: AEs with an observed or imputed date of onset on or after the infants' birth but before the start date of the first postpartum ocrelizumab infusion.

Post-ocrelizumab postpartum: AEs with an observed or imputed date of onset on or after the start date of the first postpartum ocrelizumab infusion.

Imputation of incomplete date: incomplete dates will be imputed as follows:

- If the start date is incomplete:
 - If the day is missing, impute to 01.
 - If the month is missing, impute to January.
 - If the date is completely missing, then the date will remain missing
- If the end date is incomplete:
 - If the day is missing, impute to the last day of the month
 - If the month is missing, impute to December
 - If the date is completely missing, then the date will be missing

Serious Adverse Events (SAEs): all SAEs including serious MS relapses and serious Infusion Related Reactions (IRRs).

Output Conventions

All analyses of AE data will be performed using the PTs unless otherwise specified.

For all summary tables, the AEs will be sorted by SOC (in decreasing order of overall incidence) and then by PT (in decreasing order of overall incidence). At each level of summarization (at least one event, SOC and PT), subjects reporting more than one AE will be counted only once. For AEs by grade (intensity), the highest grade will be reported.

The following summary tables will be generated for mothers and infants separately:

- Overview summary table of AEs, including: total number of subjects with at least one AE, total number of AEs, total number of deaths, total number withdrawn from study due to an AE, and total number of subjects with at least one:

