 To evaluate whether there is placental transfer of ocrelizumab from the mother to the infant 	 Serum concentration of ocrelizumab in the umbilical cord blood at birth (target time frame of blood sampling: within 1 hour after delivery) Serum concentration of ocrelizumab in the infant at Week 6 of life 	
• To evaluate whether infants potentially exposed to ocrelizumab during pregnancy are able to mount humoral immune responses to clinically relevant vaccines	 Mean titers of antibody immune response(s) to common childhood vaccinations with full or partial doses given prior to 1 year, which include responses to diphtheria, tetanus, pertussis, Hib, PCV-13, MMR, and HBV Proportion of infants with positive humoral response (seroprotective titers; as defined for the individual vaccine) to vaccines 	
 To evaluate the levels of ocrelizumab in the mother during pregnancy 	 Serum concentration of ocrelizumab in the mother during pregnancy (time frame of blood sampling: Week 24–30, Week 35) and at delivery (time frame of blood sampling: within 24 hours after delivery) 	
Safety Objectives		
 To evaluate the safety of ocrelizumab in the mother, and the safety of infants potentially exposed to ocrelizumab 	 Rate and nature of adverse events in the mother throughout the study, including changes in clinical and laboratory results Rate and nature of adverse events in the infant throughout the study, including infections and hospitalizations 	
 To evaluate pregnancy and neonatal outcomes 	 Proportion of pregnancies resulting in live births (term and preterm, with and without congenital anomalies), therapeutic abortions, or stillbirths Infant characteristics at birth, including but not limited to body weight, head circumference and length 	
Exploratory Objectives		
• To evaluate the infant's growth velocity and developmental milestones in the first year of life	 Assessment of growth velocity based on age-adjusted body length, weight and head circumference, using growth charts according to the WHO Child Growth Standards, as well as absolute values, at Months 2, 4, 6, 9, and 12 Assessment of child developmental milestones in the domains of communication, gross motor, fine motor, problem solving, and personal-social at Months 2, 4, 6, 9, and 12, using the ASQ-3 	

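### SAP 4.8.2 specifies no adverse event rate, time at risk, period denominator or confidence interval, so its by-period tables compare very unequal lengths of follow-up

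*SAP*

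**What the plan says.** **Protocol.** Table 1 (Section 2) sets the maternal safety endpoint as "Rate and nature of adverse events in the mother throughout the study", with a parallel endpoint for infants. Section 6.5 turns this into an analysis commitment: "Safety will be assessed through summaries of adverse events (including rates/incidence rates and corresponding 95% CIs) and clinical laboratory abnormalities". The same section promises two-sided Clopper-Pearson 95% intervals for the proportions of pregnancy outcomes.

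**SAP.** Section 4 says "The analyses outlined in this Statistical Analysis Plan (SAP) supersede those specified in the protocol". Section 4.8.2 presents AEs overall, by period and by maternal exposure subgroup, separately for women and infants, on the respective safety set.
- Infant periods: onset before 28 days of life, and onset from day 28.
- Women's periods: pregnancy; from birth until the first postpartum ocrelizumab infusion; from that infusion onward.
- Counting: "At each level of summarization (at least one event, SOC and PT), subjects reporting more than one AE will be counted only once". The overview table also gives the total number of AEs.

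No rate, time at risk, period-specific denominator or AE-specific interval is named. SAP 4.8.6 lists pregnancy outcomes without an interval.

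Some general wording survives. SAP Section 4 says that 95% intervals "will be presented as appropriate". SAP 4.8 speaks of incidence, and Appendix 1 keeps the infant endpoint as "Rate and nature of adverse events in the infant throughout the study, including infections and hospitalizations".

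**The concern.** The endpoint is a rate, but the governing document does not say how a rate would be formed. Over periods of unequal length, the percentage with at least one AE rises with the length of the period even when AEs occur at a constant pace. The total AE count rises with time as well, so it does not repair this.

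The period labels invite comparison: neonatal against later infancy, and before against after restarting ocrelizumab. In a small descriptive study without a control arm these tables are the safety result, and a difference due only to elapsed time could be taken for a drug or age effect.

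The denominators are open too. The summaries use the whole safety set, and nothing limits the post-ocrelizumab column to women who restarted. Protocol 3.1.4 foresees women who switch or stop therapy after birth. They have no first postpartum infusion date, on which both postpartum period definitions depend, so the period for their postpartum AEs is not explicitly defined.

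**Working it through.** Neither document gives an AE rate, expected AE count or AE precision, so there is no planned figure to reproduce. The check asks how far the by-period percentages would differ if nothing but time differed.

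**Inputs from the documents**
- Infant periods split at day 28 (SAP 4.8.2).
- AEs are reported until the last study visit (Protocol 5.1.2.1), at about 13 months of age (Protocol 3.1.4), with a +30-day window.
- Enrollment at gestational Weeks 24 to 30 (Protocol 3.1).
- First postpartum infusion at variable times; SAP 4.8.1 uses the categories 0–3, >3 to 6, and >6 months.
- About 30 evaluable infants (Protocol 6.1).

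**Assumptions**
- A constant rate r of 1 AE per person-year, with range 0.5 to 2.
- Follow-up to Month 13, restart weeks of 6, 12 and 26 as examples, and delivery at Week 40.

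**Length of follow-up.** Weeks 24–30 to Week 40 is 10 to 16 weeks, or 2.3 to 3.7 months. Adding 13 to 14 months gives 15.3 to 17.7 months, consistent with the stated participation of about 17 months (Protocol 3.2).

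**Infant periods.** 13 × 30.4375 = 395.7 days. Subtracting 28 leaves 367.7 days, or 397.7 with the window. The second period is 367.7/28 = 13.1 to 397.7/28 = 14.2 times as long as the first.

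**Formula.** P(at least one AE) = 1 − exp(−r × days/365.25).

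| Infants, r per year | 28 days | 367.7 days | Ratio |
|---|---|---|---|
| 0.5 | 3.8% | 39.5% | 10.5 |
| 1 | 7.4% | 63.5% | 8.6 |
| 2 | 14.2% | 86.6% | 6.1 |

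With the +30-day window the later figure at r = 1 is 66.3%. Over a wider assumed range, 0.02 to 0.5 per infant-month, the ratio runs from 11.8 down to 2.7.

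**Women.** Time from birth to Month 13 is 395.7/7 = 56.5 weeks. At r = 1:

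| Restart | Pre-ocrelizumab | Post-ocrelizumab | Ratio |
|---|---|---|---|
| Week 6 | 10.9% (6 weeks) | 62.0% (50.5 weeks) | 5.7 |
| Week 12 | 20.5% (12 weeks) | 57.4% (44.5 weeks) | 2.8 |
| Week 26 | 39.2% (26 weeks) | 44.3% (30.5 weeks) | 1.1 |

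Over r = 0.5 to 2 the ratio is 6.9 to 4.2 for a Week 6 restart and 1.15 to 1.09 for Week 26. Restart timing matters more than the assumed rate.

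**Total count.** For 30 infants at r = 1, person-time is 30 × 28/365.25 = 2.30 years and 30 × 367.7/365.25 = 30.2 years. About 2 and 30 AEs are expected, so the count also reflects time.

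**What a rate would show.** With those counts, 2/2.30 = 87 per 100 infant-years (exact Poisson 95% interval 10.5 to 314), and 30/30.2 = 99 (67 to 142). The same data as subjects with an event would be about 2/30 (7%) and 19/30 (63%). The apparent difference disappears, and the neonatal interval shows how little information that period holds.

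**The case against.** The strongest reply is that the SAP has not abandoned anything. Its general sentence on 95% intervals, its use of incidence and its retained rate endpoint leave room to report AE rates. The protocol's own phrase is undefined and could mean the proportion with an event, so neither document promises person-years or Poisson intervals. All of that stands. A reader might infer that the SAP removes rates and intervals; the supported statement is that it never specifies them. But either meaning calls for an interval that SAP 4.8.2 does not name. Elsewhere the SAP is specific: Clopper-Pearson for the primary endpoint (4.4.2) and an optional annualized relapse rate with a 95% interval (4.6.4).

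Four other stronger readings are tempting and are not supported:
- **That only subject counts are given.** The overview table also has the total number of AEs, although without a time denominator.
- **That all AE tables are distorted.** The overall and maternal-exposure tables have no planned difference in follow-up. No tests or period comparisons are planned, so the risk lies in how the by-period tables are read.
- **That women who never restart count as pre-ocrelizumab for the whole year.** The text leaves them without an explicit assignment; it does not place them there.
- **That the exposure rule in SAP 4.8.1 inflates AE follow-up.** The limit at "date of last OCR dose plus risk window of 6 months (182 days") belongs to treatment duration in the exposure table. No AE table uses it, and it does not cap the post-ocrelizumab AE period.

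**Conclusion.** The point holds as a gap in specification. SAP 4.8.2 does not carry out the protocol's commitment to AE rates with 95% intervals, and does not state or justify a departure. As written, the by-period tables would show differences that come from elapsed time alone.

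For infants the effect is large at every rate considered: about 7% against 63% at 1 AE per infant-year. For women it ranges from about 5.7-fold to almost none as restart moves from Week 6 to Week 26, so a general claim of severalfold distortion in women would go too far. These sizes rest on an assumed constant rate that is in neither document; true rates may differ between pregnancy, the neonatal period and later.

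The primary endpoint is not affected. This is a cheap improvement to descriptive safety tables.

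Separately, and minor: the end date for treatment duration in SAP 4.8.1 is labelled as last contact but omits study discontinuation. That affects the exposure table only.

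**What to change.** In SAP 4.8.2, for the by-period tables:
- State the number entering each period. Use only women who restarted for the post-ocrelizumab period, and explicitly assign women who never restart.
- Give person-time, and events per 100 person-years with exact Poisson 95% intervals, for all AEs, serious AEs and infections.
- End person-time at the earliest of period end, study discontinuation or last visit, death, and data cut-off.

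In SAP 4.8.6, carry over the Clopper-Pearson 95% intervals for pregnancy outcomes from Protocol 6.5. In SAP 4.8.1, add study discontinuation to the treatment-duration end date. If the sponsor prefers not to report rates, the SAP should state and justify the departure from Protocol 6.5.

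The cost is SAP wording and modest extra programming, with no new data collection. The intervals will be wide with about 33 women, which is itself useful to the reader.

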4.8.3 Laboratory Data

Laboratory assessments (performed in central laboratory, except for urinalysis) will include the following:

- **Haematology (Women)**: hemoglobin, hematocrit, quantitative platelet count, red blood cell (RBC) count, white blood cell (WBC), absolute or/and differential count [neutrophils, eosinophils, lymphocytes, monocytes, basophils].
- **Serum chemistry (Women):** potassium, sodium, chloride, random glucose, AST, LT, gamma-glutamyl transpeptidase (GGT), total bilirubin and creatinine.
- **Urinalysis (Women):** using urine dipstick at site; may include pH, specific gravity, glucose, protein, ketones, blood, and microscopic examination (sediment, RBCs, WBCs, casts, crystals, epithelial cells, bacteria) at the discretion of the investigator.
- Hepatitis B virus serology (Women): Women with positive screening tests for HBV, determined by a positive hepatitis B surface antigen (HBsAg) result (current infection) or positive hepatitis B core antibody (HBcAb) titers (previous infection) will

be excluded. Women with documented history of HBV vaccination or positive HBsAb titers are eligible.

- Serum immunoglobulin (Ig) concentration (Women)
- Serum antibody (IgG) titers to immunizations (Women) for measles, mumps, rubella, TT, diphtheria, pertussis, varicella zoster, Streptococcus pneumoniae, HBV and SARS-CoV-2 (along with nucleocapsid and spike protein titers; only for those mothers who have received the vaccine, as per local clinical practice) will be performed.
- Serum antibody (IgG) titers to immunizations (Infant): May include but not be limited to MMR, DTaP, Hib, PCV-13, and HBV; 1 month after the first dose of MMR vaccine, or at month 13 (±30 days) if MMR vaccine is not planned to be administered.
- Lymphocyte subtypes (Women and Infant): Blood samples will be collected to measure B-cell counts (CD19+) and B-cell subsets (Appendix 3), T-cell counts (CD3+, CD4+, CD8+) and natural killer NK cell counts (CD16+, CD56+).
- **Ocrelizumab concentration (Women and Infant):** serum samples will be collected for determination of ocrelizumab concentration.
- **sNfL (Women)**: samples will be collected for determination of sNfL, as described in Section 4.6.5.

4.8.3.1 General laboratory evaluation

All laboratory assessments in the women (hematology, serum chemistry, urinalysis, HBV serology and serum immunoglobulin concentration) will be summarized in the SAFW or listed when applicable.

Absolute values and change from baseline at each visit will be summarized using standard unit. The baseline value for laboratory assessments summarized in women will be the last value prior to the first dose of study medication. When laboratory data are presented over time, these laboratory values will be time-windowed into a common visit structure. If multiple values of the same laboratory parameter occur within the same time window, the worst value for that parameter will be presented in the summary table.

Unless specified otherwise, any laboratory parameters which are BLQ will be listed, for summaries a value of the LLQ/2 will be imputed. Values above the upper limit of quantification will be summarized at the upper limit of quantification.

For hematology and serum chemistry, the number and percentage of patients with normal/abnormal laboratory outcomes based on normal laboratory ranges will be summarized for each parameter and visit. For urinalysis, the number and percentage with each test result category will be reported for each parameter and visit.

Corresponding patient-level listings will be produced for the following in the SAFW: haematology, serum immunoglobin concentration, laboratory abnormalities for

haematology, laboratory abnormalities for serum chemistry, laboratory abnormalities for uinalysis.

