4.1 ANALYSIS SETS

4.1.1 Full Analysis Set (Women)

The full analysis set of women (FASW) will include all enrolled pregnant who were exposed to ocrelizumab either 0-6 months before the LMP or in the first-trimester of pregnancy (i.e., up to gestational Week 13 [inclusive]). This corresponds to 13*7+6, 97 days, as the last day of the first trimester.

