 - Number of relapses before, during pregnancy (defined by LMP) and after pregnancy (defined as after birth) will be summarized in 3-month interval respectively.
 - Number and percentage of women in each category (0, 1, 2, 3 and ≥4) in
 3-month intervals of before/during/after pregnancy.
 - Number of relapses after first OCR and up to 1 year before pregnancy, during pregnancy, up to 1 year after delivery will be presented. Annualized relapse

rate and 95% CI may also be presented if warranted by the number of data points.

- Mean EDSS score in 3-month interval of before/during/after pregnancy. In case of multiple EDSS score at the same visit, the median will be used.
- Change from baseline in EDSS by visit.
- Presence of any clinically significant abnormalities from the neurological examination (Yes, No) by visit
- Type of neurological abnormality (disability progression independent of relapse, MS relapse, signs or symptoms suggestive of Progressive Multifocal Leukoencephalopathy, Other) by visit

MS relapses, EDSS and neurological examination findings will also be listed. Analysis will also be presented for subgroups based on OCR exposure prior to the study as list in Section 4.5.4.

4.6.5 Women's Neuroaxonal Damage

To detect presence of neuroaxonal damage in the mother during pregnancy and postpartum, serum neurofilament light chain (sNfL) levels are measured at baseline (gestational age Week 24-30), gestational age Week 35, at delivery and postpartum (in line with ocrelizumab administration timepoints). Absolute sNfL levels will be log (base 10) transformed. The geometric mean with corresponding 95% CI and change from baseline will be back transformed and presented. Absolute sNfL levels as well as change from baseline based on log back transformed may also be displayed graphically over time, as appropriate.

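### SAP 4.8.3.1 anchors the maternal laboratory baseline to a first dose of study medication, which gives a late, missing or impossible baseline in this study; it should be the Week 24–30 visit

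*SAP*

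**What the plan says.** SAP 4.8.3.1 covers maternal hematology, chemistry, urinalysis, hepatitis B serology and immunoglobulin in the women's safety set. That set equals the women's full analysis set (SAP 4.1.3), so it is not limited to women who resume treatment.

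- The baseline rule is: "The baseline value for laboratory assessments summarized in women will be the last value prior to the first dose of study medication".
- The output that depends on it is: "Absolute values and change from baseline at each visit will be summarized using standard unit".
- Where several values fall in one window, "the worst value for that parameter will be presented in the summary table".

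Other sections of the SAP place baseline at the screening visit in pregnancy. SAP 4.6.5 says sNfL "levels are measured at baseline (gestational age Week 24-30), gestational age Week 35, at delivery and postpartum". SAP 4.8.1 says "Ocrelizumab will not be administered post-baseline until the infant's birth", which puts baseline before birth. SAP 4.8.7 defines concomitant medication relative to the baseline visit. Protocol 3.1.2 combines baseline with screening at gestational Weeks 24–30.

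**The concern.** The rule reads like standard wording for a trial in which treatment starts after baseline sampling. Here the study treatment is commercial ocrelizumab (Protocol 4.3). Every woman has received it before enrollment, none may receive it between enrollment and birth, and restarting it afterwards is optional. The phrase could therefore point to a dose before the study or to the first postpartum dose, and the SAP does not choose.

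Laboratory changes form part of the maternal safety endpoint (Protocol Section 2, Table 1). A programmer who follows the rule literally would produce a table mixing forward and backward differences and leaving out women who never resume, or would find that no table can be built. The protocol's baseline visit does not settle the matter, because SAP Section 4 says: "The analyses outlined in this Statistical Analysis Plan (SAP) supersede those specified in the protocol".

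**Working it through.** The plan gives no figure for this point, so the check compares the order of doses and samples under each reading.

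**Inputs**

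- Last permitted exposure: SAP 4.1.1 says "This corresponds to 13*7+6, 97 days, as the last day of the first trimester". This reproduces: 13 × 7 + 6 = 97.
- First scheduled maternal sample: gestational Weeks 24–30 (Protocol 4.5.2.7). The earliest day is 24 × 7 = 168; the latest is 30 × 7 + 6 = 216.
- Later samples: Week 35 ± 14 days (Weeks 33–37), then Infusion 1 and Infusion 2. Immunoglobulin is also drawn at delivery.
- Draw time at the infusion visits: Protocol Appendix 1, footnote y, puts immunoglobulin before the methylprednisolone. No draw time is stated for hematology or chemistry.
- Women who stop or switch disease-modifying therapy after birth have no further maternal laboratory assessments (Protocol 3.1.4).
- Planned number of women: 33.

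**Reading 1: first postpartum dose**

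SAP 4.8.1 supports this reading, since it counts treatment duration from the "Date of first postpartum dose". For immunoglobulin, baseline is then the Infusion 1 sample. For hematology and chemistry it is Infusion 1, or Week 35 if the Infusion 1 sample is drawn after the infusion starts. For a woman who resumes:

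| Sample | Baseline at Infusion 1 | Baseline at Week 35 (hematology, chemistry) | Baseline at Weeks 24–30 |
|---|---|---|---|
| Weeks 24–30 | backward difference | backward difference | baseline |
| Week 35 | backward difference | zero | change |
| Delivery (immunoglobulin only) | backward difference | not applicable | change |
| Infusion 1 | zero | change | change |
| Infusion 2 | change | change | change |

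A Week 35 baseline is 33 − 30 = 3 to 37 − 24 = 13 weeks after the study's baseline visit. An Infusion 1 baseline cannot precede birth. For an assumed delivery at 37 weeks, birth is 37 − 30 = 7 to 37 − 24 = 13 weeks after that visit; for an assumed delivery at 40 weeks it is 10 to 16 weeks after.

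A woman who does not resume has no anchor dose and so no baseline. With r the share resuming (not in the documents, so assumed), the number affected is 33 × (1 − r):

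- r = 0.9: 33 × 0.1 = 3.3, about 3 women
- r = 0.7: 33 × 0.3 = 9.9, about 10 women
- r = 0.5: 33 × 0.5 = 16.5, about 17 women

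These women lose the Week 35 change (hematology, chemistry, immunoglobulin) and the delivery change (immunoglobulin). After stopping or switching therapy they have no later scheduled maternal laboratory visit, so these are the only scheduled changes they could have contributed.

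**Reading 2: a dose before enrollment**

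The gap from the last permitted exposure to the first scheduled sample is 168 − 97 = 71 days at the least, and 216 − 97 = 119 days for the latest permitted exposure with sampling at the end of Week 30. A woman's first dose is no later than her last. No scheduled study value can precede it, so 33 of 33 women have no baseline.

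**The case against.** The strongest reply is that the postpartum reading is plainly intended. SAP 4.8.1 concerns postpartum exposure, SAP 4.8.2 splits maternal adverse events at the first postpartum infusion, and earlier ocrelizumab is summarized as history in SAP 4.3.1. On that reading a value taken just before re-exposure is a coherent reference, changes may be meant only for visits after it, and the SAP is silent about women who do not resume rather than excluding them. The supersession statement concerns analyses and does not abolish the baseline visit. The tables are descriptive, the number of women is small, and the resumption shares have no basis in the documents.

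Much of this is fair. The postpartum reading is the likelier one, the 33-of-33 result belongs only to the other reading, and the 3, 10 or 17 women illustrate a range rather than estimate it. A reference before the infusion is useful for what follows that infusion.

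The defect remains. If only visits after baseline count, the pregnancy changes drop out for every woman whose baseline is Infusion 1, leaving Infusion 2 as the one scheduled visit with a change. Any baseline for women who do not resume would have to be invented by the programmer. And the SAP's own use of the Week 24–30 visit elsewhere makes the laboratory rule inconsistent within the document.

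**Conclusion.** The concern holds. The baseline rule as written gives a late baseline for women who resume ocrelizumab and none for those who do not, or gives no baseline to anyone, depending on the reading. The first part does not depend on the resumption rate: even if all 33 women resume, the pregnancy values are not measured against the Week 24–30 visit. Only the number without a baseline rests on the assumed rate.

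The effect is limited to descriptive change-from-baseline summaries of maternal hematology, chemistry and immunoglobulin. Absolute values, normal/abnormal counts, listings, lymphocytes, sNfL, investigator-reported liver events and the infant primary endpoint are unaffected. The rule should be corrected before the tables are programmed, but it does not threaten the study's main conclusion.

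**What to change.** In SAP 4.8.3.1, replace the baseline sentence with:

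> Baseline for maternal laboratory assessments is the value at the gestational Week 24–30 screening/baseline visit (the last value if retested). This value is also the one displayed for the baseline visit, and the worst-value rule applies to post-baseline windows only.

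Every woman with a screening sample then has a baseline, and women who do not resume ocrelizumab contribute changes at Week 35 and, for immunoglobulin, at delivery. The clause on the worst-value rule is needed because Protocol 4.1.2 allows one retest of an abnormal screening value; without it, the baseline displayed could differ from the baseline used to compute change.

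If a view of change after the infusion is wanted, add a separately labelled reference: the last value before the first postpartum ocrelizumab infusion, used only for later assessments in women who resume.

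The cost is one SAP sentence, or two with the optional reference, and minor programming. No new data are needed.
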